13.0 Genetic Analysis Information NA

14.0 Sharing of Results with Participants NA

15.0 Risks to Participants*

The anticipated increase of activity places the participant at greater risk for hypoglycemia. As the participants increase their activity they should be aware of the guidelines to avoid/treat hypoglycemia and frequent adjustments to their insulin regimen may need to be made. The frequent adjustments may also lead to increased contact with the diabetes team. Participants will be surveyed about their level of stress, potentially leading to emotional discomfort. The participant must wear the watch every day throughout the study, must follow prompts provided by the watch, and charge it as frequent as every 2-3 days. These elements may cause inconvenience and/or discomfort. Per the device manual, there are additional risks if the device is not used appropriately, including rare risks of fire, chemical burn, electrolyte leak, and/ or injury, and health risks such as interfering with pacemakers, triggering seizures, and irritating skin. Because the research requires the collection of identifying data, there is a risk of breach in confidentiality.

SHORT TITLE:

16.0 Potential Benefits*

There may not be direct benefits from taking part in the research. However, as the participants with T1D react to the watch interventions, they may become more active and more aware of stress throughout the day. As these elements improve, participants may see improvement in self-care, diabetes management, HbA1c, and decreased potential for long-term diabetes complications. There is no direct benefit for the parents of participants with T1D. The knowledge gained from this study may help other healthcare providers know how to better serve their patients by utilizing Garmin trackers or similar products to promote activity.

17.0 Investigator Assessment of Risk/Benefits Ratio*

17.1 *Please provide an assessment of risk and benefits in the table below. Note, the IRB makes the final determination based upon responses in the two preceding sections.*

Select as applicable:	Pediatric Risk Category:	
	Category 1	Research not involving greater than minimal risk (45 CFR §46.404 and 21 CFR §50.51)
	Category 2	Research involving greater than minimal risk but presenting the prospect of direct benefit to the individual participants. (45 CFR §46.405 and 21 CFR §50.52)
	Category 3	Research involving greater than minimal risk and no prospect of direct benefit to individual participants, but likely to yield generalizable knowledge about the participant's disorder or condition. (45 CFR §46.406 and 21 CFR §50.53)
	Category 4	Research not otherwise approvable which presents an opportunity to understand, prevent, or alleviate a serious problem affecting the health or welfare of children. (45 CFR §46.407 and 21 CFR §50.54)
Select if applicable:	Adult Risk Category:	
	Not Greater than Minimal Risk	
	Greater than Minimal Risk	

18.0 Payment, Reimbursement and Tangible Property Provided to Participants*

18.1 Is payment, reimbursement, or tangible property part of the study?

SHORT TITLE:

Yes No *(If No, delete the following subsections)*

18.2 Payment to Participants:

CCPay
 Gift Card: (Merchant: _____)
 Other: _____

Note: "Gift Card" and "Other" options require approval by Research Administration. Upon submission in myIRB, ORI staff will initiate the Research Administration approval process.

18.3 Payment Schedule:

Day 1 Surveys	Day 180 Surveys	Day 365 Surveys	Total Compensation Possible
\$15	\$15	\$15	\$45

18.4 Reimbursement: NA

CCPay
 Check
 Other: _____

18.5 Tangible Property:

The participants will be given a Garmin tracking device (value 129.99\$) when they begin the study, and we will let the participant keep the device after study completion.

19.0 Compensation for Research-Related Injury NA

20.0 Economic Burden to Participants NA

21.0 Parental Permission and Adult Consent Process*

Parents/ participants will be contacted and asked for verbal consent to participate in the study per CM policy.

We will call the parent/participant and ask if they want to be emailed the study information letter to read over (via a CM approved email server). We will ask that if they are interested in participation, that they call us back to discuss the study in more detail. We will ensure the participant has plenty of time to consider the study and ask questions. They will be told they don't have to participate. We will ask questions to

SHORT TITLE:

make sure they understand the study. We will follow the CM policy on obtaining p/a/c.

To facilitate an ongoing consent discussion, the Information Letter will be included with the mid-point (day 180) REDCap survey.

21.1 *Indicate below all methods of Permission/Consent that will be used in this study.*

Waiver of Documentation of Permission/Consent

Permission/Consent form provided but signature will **NOT** be obtained (e.g. verbal consent)

Must complete [Addendum A: Waiver of Documentation of Permission/Consent](#)

Waiver of written documentation of permission of parent/LAR for pediatric participants

Study group(s) to which this method applies: Parent of Participants 8-17 years old

Waiver of written documentation of consent of adult participants

Study group(s) to which this method applies: Participants 18 and above and Parent as a Participant

Waiver of written documentation of consent of participants turning 18

Study group(s) to which this method applies: If a child participant reaches the age of majority (18 years old) during the study, he/she will be asked to again provide verbal consent if they wish to remain on the study.

Additional Methods

Obtaining permission/assent/consent of non-English speaking parents or participants

Must compete [Addendum C: Non-English Speaking Participants](#)

Study group(s) to which this method applies:

21.2 Permission/Consent/Consent at 18 Discussion:

Permission/Consent Discussion:

SHORT TITLE:

Consent at 18 Discussion: Participants who turn 18 while active in the study will be contacted and asked for verbal consent to continue to participate in the study. We will contact the participant and email them the study information letter to read over (via a CM approved email server). We will ask that if they are interested in continuing participation, that they call us back to discuss the study in more detail. We will ensure the participant has plenty of time to consider the study and ask questions. They will be told they don't have to participate. We will ask questions to make sure they understand the study. We will follow the CM policy on obtaining p/a/c.

21.3 Documentation of Permission/Consent/Consent at 18: NA

21.4 Identification of Participants turning 18: Participant age will be tracked on a master log. It will be assessed at enrollment if the participant will still be active in the study when they turn 18. A reminder will be put on the calendar for that day to contact and obtain verbal consent via the Adult consent. We will attempt to reconsent the participant as an adult up to three times. During the reconsent period we will mark the participant record as "reconsenting" and not collect any study data about the participant until they reconsent. If they have not consented after the third contact, we will remove the participant record from the study database.

22.0 Assent of Pediatric Participants

22.1 Select the option(s) that apply to the study:

Assent of pediatric participants WILL BE SOUGHT following assessment of ability to assent.

Obtaining assent of pediatric participants is NOT POSSIBLE due to:

- The capability of the participants (considering the ages, maturity, physical and/or psychological state) is so limited that they cannot reasonably be consulted.*
- The intervention or procedure involved in the research holds out a prospect of direct benefit that is important to the health or well-being of the participants and is available only in the context of the research.*

Obtaining assent of pediatric participants is NOT PRACTICLE given the context of this study (e.g., minimal risk, no direct contact with participants).

Must complete Addendum B: Waiver/Alteration of Permission/Assent/Consent

SHORT TITLE:

22.2 Assessment of Ability to Assent:

Ability to assent will be discussed with the parent/LAR and clinical care team to confirm the pediatric patient is able to understand the study and procedures.

22.3 Assent Discussion: The parent of the child will be contacted via telephone and asked if they want to be emailed the study information letter to read over (via a CM approved email server). The parent will be instructed to call back with the child if they are interested in participating to discuss the study in more detail. If the parent and child feel more comfortable discussing the study in person, the discussion will be conducted in person. The parent and child will have plenty of time to consider the study and ask questions. They will be told they don't have to participate. They will be asked questions to make sure they understand the study. The CM policy on obtaining p/a/c will be followed.

To facilitate an ongoing consent discussion, the Information Letter will be included with the mid-point (day 180) REDCap survey.

22.4 Documentation of Assent or Inability to Assent:

We will follow CM Research Policy on obtaining permission/ assent/ consent and research documentation in the Electronic Health Record

23.0 HIPAA and Confidentiality

HIPAA regulations apply to this study if the data used or accessed relates to:

- The past, present, or future physical or mental health or condition of an individual;
- The provision of health care to an individual; **OR**
- The payment for the provision of health care, **AND**
- identifies the individual or for which there is a reasonable basis to believe it can be used to identify the individual.

23.1 HIPAA Authorization

a. *Full Written HIPAA Authorization will be obtained (within the p/a/c form or standalone form)*

Partial Waiver of HIPAA Authorization (e.g. waiver for recruitment and pre-screening purposes only)

Must complete Addendum E: Waiver/Alteration of HIPAA Authorization

SHORT TITLE:

a) We will need to access their MRN, name, DOB, email and phone number for prescreening/recruitment purposes.

Alteration of HIPAA Authorization (some but not all required elements of an Authorization are present, e.g. signature will not be obtained)
Must complete [Addendum E: Waiver/Alteration of HIPAA Authorization](#)

a) We will obtain verbal consent as this is minimal risk study.

Waiver of HIPAA Authorization (authorization will NOT be obtained)

If Other, explain:

23.2 Specify the PHI for which accessing (“viewing”) or recording (“writing down”) is necessary for the purpose of this research:

1. Name/Initials	 Accessed only	 Recorded
2. All elements of date (except year) directly related to an individual (e.g. date of birth, admission date, discharge date, date of death)	 Accessed only	 Recorded
3. Medical record number	 Accessed only	 Recorded
4. Account number	 Accessed only	 Recorded
5. Health plan identification number	 Accessed only	 Recorded
6. Social Security Number	 Accessed only	 Recorded
7. Device identifiers and serial number	 Accessed only	 Recorded
8. Certificate/License number	 Accessed only	 Recorded
9. Telephone number	 Accessed only	 Recorded
10. Fax number	 Accessed only	 Recorded
11. Email addresses	 Accessed only	 Recorded
12. Web addresses (URLs); Internet IP addresses	 Accessed only	 Recorded
13. Street address, city, county, precinct, zip code or equivalent geographical codes	 Accessed only	 Recorded
14. Full face photographic images and any comparable images	 Accessed only	 Recorded
15. Biometric identifiers, including finger and voice print	 Accessed only	 Recorded
16. Vehicle identifiers and serial numbers, including license plate number	 Accessed only	 Recorded

SHORT TITLE:

17. Any other unique identifying number, characteristic or code that may help identify individual participants including their initials (e.g. student or employee ID number)	 Accessed only	 Recorded
18. Elements of date, including year, for persons 90 years or older	 Accessed only	 Recorded
19. Other: Garmin Connect account token number, CGM device (for data collection), insurance type (public vs private)	 Accessed only	 Recorded

23.3 Information Security

Only those working on the study will have access to the study data. The master list will be stored securely on the secure CMH Microsoft Azure Cloud (including Teams, Sharepoint, and OneDrive) with access restricted to research team members. Some additional data (such as correspondence) will be kept in the secure study file drive on the CMH network domain, and also in CM approved platforms (such as the SSN in the payment system for study payments). The minimum amount of PHI will be used for this study, and will be destroyed at the earliest possible time at completion of study after data analysis. The access to the REDCap study database will be protected by limiting access to the study team only. The prescreening log and subject log will be stored in the secure limited access study database with the study data sheets. The subject log may include the child's name, date of birth, child's medical record number, date consented, date of service, email address, phone number and study ID number. After the minimum length of time has lapsed (one to two years post study closure depending on the space needs of the team) physical records may be transferred to hospital approved offsite facility.

23.4 Certificate of confidentiality:

No Certificate of Confidentiality has been issued for this study.

24.0 Provisions to Protect the Privacy Interests of Participants*

24.1 Participants will be contacted via phone to discuss enrollment into the study. If they prefer an in-person discussion, they can be approached and consented at the CM endocrine clinic. They will be given as much time needed to review the study information sheet and ask questions before deciding whether to participate. They

SHORT TITLE:

will be told this is voluntary, and enrolled subjects will be informed that they may withdraw at any time without penalty or loss of benefits. Any new information gathered during the study that may impact the subject desire to continue in the study, will be revealed as soon as it becomes available. Communication may include emails (per CM communication policy) or texting (via the Health Device Portal Messaging system). Follow up visits will be conducted remotely via phone, unless the patient requests in person visits, which will be held in the endocrinology offices. Follow-up may also occur via emails (per CM communication policy) or via texts (via the Health Device Portal messaging system). Recruitment may occur via the clinic intake form asking if the participant would like to join the observational study (see attached form).

The subject study ID will be used to set up the Garmin account for all participants, with no personal information (PII or PHI) used. This will keep private information used in the study will remain secure in the study database.

25.0 Withdrawal of Participants*

Participants may withdraw from the study at any time at their own request, or they may be withdrawn at any time at the discretion of the investigator. Reasons for withdrawal may include:

- Participant no longer wants to participate in study visits/procedures/processes.
- Participant's clinical care deciding it is not in their best interest to continue participation
- Participant stops providing information and cannot be reached by the research staff. For example, lost to follow up after three active attempts to contact participant (not including automated alerts, for example the automatic texts triggered when watches are inactive)

If a participant is withdrawn or lost to follow up, this will be documented appropriately in the REDCap database developed for research documentation since this study may not be recorded in the medical record per CMH policy.

All data collected prior to the participant withdrawal will be retained.

DATA MANAGEMENT

26.0 Data Collection*

This study will be completely integrated into the Diabetes Data Dock at CMKC. Data will be collected and paired with the other wearable devices, such as pump and continuous glucose monitor readings.

SHORT TITLE:

Surveys (IPAQ, HFS-II/P) will be collected at baseline and EOS. Data collected from EMR will include medical history, lab results, demographics, clinical data, insurance type (public vs private).

Child/ adult participant data -

Demographic data: We will use the REDCap demographics survey to collect demographic data. We may use the Diabetes Data Dock and/or the child's electronic health record to verify or extend demographic data (e.g., T1D diagnosis, history of T1D-related complications, T1D regimen, shipping address to send the Garmin Device, shipping history).

HbA1c data: We will use routine T1D care POC HbA1c levels to at baseline and at post-treatment (~3 months post baseline).

CGM or SMBG data: Families will use their personal, prescribed CGM or standard blood glucose monitor (SMBG) throughout the study. Families will share CGM data with the study team using their personal, CM connected account. Data will be download automatically to the Diabetes Data Dock using API.

Insulin delivery data: Participants will use their personal, prescribed insulin delivery device throughout the study. Participants and parents/LARs of adolescents will share participants' insulin device data with the study team using their personal, CM connected account.

Questionnaire data: We will use REDCap to electronically collect any survey data, including participants' daily activity schedules. We will use a single REDCap database for all study participants. This REDCap data base will reside on a CM secured server.

Garmin data and activity monitor: Data will be downloaded and stored on the Diabetes Data Dock using API connection. Primary physical data will be gathered from the Garmin Connect platform. The anonymous participant Garmin data from the Garmin Connect platform will be loaded to a secure database through the Garmin Health API connection developed by Children's Mercy Research Informatics. The Garmin tracker will not collect personal information. Also, the patient study record will be linked to the Garmin tracker. The Garmin Health Portal attached to the Garmin Health API will also contain the communication texted to the participants (if any). The interventionist team will be able to pull the data to Microsoft Azure database to evaluate. Clinical data will also be collected from EMR.

Parent Data -

Demographic data: We will use the REDCap demographics survey to collect demographic data. We may use the Diabetes Data Dock and/or the child's electronic health record to verify or extend parent demographic data (e.g., shipping address to send the Garmin Device, shipping history, contact information, etc.).

SHORT TITLE:

Sensitive Data: Adult participants with T1D will be asked in the HFS if they avoided sex to prevent a hypoglycemic event. All participants will be asked about physical activity and efforts to prevent hypoglycemic incidents, which can be sensitive topics. Participants will be assured in the consent letters that they do not need to answer any questions they want to, and answers will be kept in confidence.

A horizontal row of 30 empty square boxes for writing responses.

27.0 Adverse Events and Unanticipated Problems*

27.1 Monitoring:

Participants/families will be instructed to contact the team if an adverse event or other unanticipated problem occurs.

27.2 Reporting:

We will follow the CM policy on reportable events to report adverse events and other unanticipated problems to the CM IRB.

28.0 Statistical Analysis*

28.1 Matched Cohort:

Where possible, the intervention group will be compared to a matched cohort identified using propensity score matching. The propensity score for the groups will take into consideration age, baseline HbA1c, duration of diabetes, insurance, race, device usage, and time in range.

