2.0 Objectives*

2.1 Primary Objectives:

1. Measure physical activity and sleep for up to 365 (\pm 30 days) days using a Garmin physical activity tracker among youth and young adults with T1D.
2. Evaluate the impact of physical activity and sleep related variables on rate of DKA admission over 90 and 180, and 365 \pm 30 days
3. Evaluate the impact of physical activity and sleep related variables on change in Time in Range and other continuous glucose monitor-derived metrics of glycemic control over 90, 180, and 365 \pm 30 days
4. Test the impact of physical activity and sleep related variables on machine learning models to predict change in HbA1c, DKA admissions, and change in Time in Range over 90, 180 and 365 \pm 30 days

2.2 Secondary Objectives:

1. Examine for correlations between self-reported physical activity (IPAQ), hypoglycemia fear (HFS-II), and parent hypoglycemia fear (HFS-P) at 0, 6, and 12 months after study enrollment.
2. Evaluate any change in physical activity levels via self-report with the IPAQ survey (to allow comparisons to external cohorts).
3. Evaluate any change in how participants feel about episodes of hypoglycemia while wearing the Garmin physical activity tracker via the Hypoglycemic Fear Scale II (HFS-II)
4. Evaluate any change in how parents feel about episodes of hypoglycemia in their children wearing the Garmin physical activity tracker via the Hypoglycemic Fear Scale II for Parents (HFS-P)

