4.0 Study Endpoints

1. Minutes/day of Moderate-to-vigorous physical activity (MVPA) – from Garmin device over 30, 90, 180, and 365 ± 30 days
2. Sleep minutes/day – derived from Garmin device over 30, 90, 180, and 365 ± 30 days
3. Other activity metrics derived from Garmin device over 30, 90, 180, and 365 ± 30 days
4. HbA1c – collected from Electronic Medical Record, obtained via standard care (binned as 46-135 days, 136-225 days, 226-305 days, and 306-410 days)
5. Hospital admissions for DKA (0-180 days and $181-365 \pm 30$ days)
6. 14-day Time in Range and other CGM-derived metrics of the quality of glycemic control over 30, 90, 180, and 365 ± 30 days
7. Model performance characteristics (e.g. precision, recall, F1) of predictive models for the outcomes listed in 4.1-4.6

5.0 Study Design*Participants with T1D treated at the Children's Mercy Endocrine clinic aged 8-21 years old will be asked to wear a Garmin VivoSmart 4 (or later) physical activity tracker for at least 6 months. This tracker will collect detailed physical activity and sleep data as measured by moderate to vigorous physical activity (MVPA) and sleep minutes/day. The tracker collects heart rate and accelerometry data, collected into the Garmin Connect application. The diabetes center will use the Garmin Health API connection developed by Children's Mercy Research Informatics to extract the data into a data warehouse in Microsoft Azure (CMH account). As noted in previous studies, MVPA is automatically measured by the tracker when the wearer runs for >1 minute or walks for >10 consecutive minutes. The weekly MVPA and step count are both weighted by multiplying the mean of weekday activity by 5, adding it to the mean of weekend activity and dividing the sum by 7.

$$\text{Weighted MVPA} = \frac{[(\text{MVPA}) \times 5] + (\text{MWVPA})}{7}$$

$$\text{Weighted step count} = \frac{[(\text{MSC}) \times 5] + (\text{MSC weekend})}{7}$$

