6.0 Study Interventions*

6.1 Description: The Garmin VivoSmart 4 (or later) physical activity tracker is worn like a watch on the user. The tracker assesses several physical states (i.e., HRV, sleep, and activity) to provide the participants with a “Body Battery” measure. This measure indicates either when the body is at optimal time for activity, or if the individual needs to rest. The tracker also monitors stress levels using heart rate variability (HRV) and provides a reminder alert to “*Take a moment to breathe.*” The tracker utilizes behavioral principles to set goals with participants based on previously completed activity. To meet these goals the tracker alerts participants after a period of inactivity, encourages regular movement throughout the day, and decreases the amount of time spent sedentary.

6.2 Behavioral Intervention: The Garmin VivoSmart 4 (or later) physical activity tracker will be part of a behavioral intervention with accepted standard of care that will help improve activity behaviors and decrease stress. This is done by prompting the participant to engage in activity when sedentary and/or stressed.

6.3 Drugs, Biologics, or Devices:

Drug/Biologic/Device Name	Describe how the article is being used under current FDA approved labeling
Garmin VivoSmart 4 (or later)	This device will be continually used to monitor participants activity and sleep.
Garmin Connect App	This app will be used by the diabetes team interventionists to monitor the data collected via the device.

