8.0 Local Number of Participants

We will pre-screen up to 1000 participants, depending on the patients coming to the diabetes clinic. If patients meet the requirements for the study, they will be sent the information letter.

	Group 1: Pre-screening/screen failures	Group 2: participant	Group 3: parent of participant	Totals

SHORT TITLE:

Enrollment Goal: Number of participants to be enrolled = the number of participants to be consented	1000	200	100	1000 pre-screened for a total enrollment goal of 300
----------------------------------------------------------------------------------------------------------------------	------	-----	-----	------------------------------------------------------

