11.0 Additional Study Activities NA Blood and Other Specimen Collection: NA

12.0 Follow-up

After the V1D1 visit, physical activity information will be collected from the participant trackers via the Garmin Connect app and uploaded into storage via the Garmin Health API connection developed by Children's Mercy Research Informatics. If the participant experiences any issues with tracker activation or use, additional study visits will be scheduled at Visit 2, Visit 3 and Visit 4 (approximately Day 14, 28, or 52).

Participants will have information collected from the devices until 365 (+/- 30 days) days following start of study, at which point they will have one more SOC clinic visit, complete surveys, and then will have completed the study requirements. There will not be any research follow up after this point, and if the participants elect to discontinue from the study, there will be no follow up. When participants complete the study requirements or elect to discontinue, they will be marked as such in the RedCap database of study participants. We will ask the patients if they are willing to complete the surveys prior to discontinuing the study.

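### The matched-cohort comparison in Section 28.1 estimates the effect of being in the tracker group, not the impact of activity and sleep that primary Objectives 2 and 3 ask about

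*Combined protocol and SAP*

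**What the plan says.** Section 28.1 (Matched Cohort) states: "Where possible, the intervention group will be compared to a matched cohort identified using propensity score matching". The propensity score uses "age, baseline HbA1c, duration of diabetes, insurance, race, device usage, and time in range". Section 28.1 names no outcome, objective, matching ratio or source for the cohort. The text available for review ends at this subsection.

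Section 2.1 lists four primary objectives. Objective 2 reads "Evaluate the impact of physical activity and sleep related variables on rate of DKA admission over 90 and 180, and 365" days. Objective 3 asks the same of change in time in range (TIR) and other CGM metrics. Objective 4 asks what the activity and sleep variables do for machine-learning models of HbA1c change, DKA admissions and TIR change. Section 4.0, item 7, gives example performance measures for predictive models.

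Four other places bear on who is compared:

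- Section 6.2 says the "physical activity tracker will be part of a behavioral intervention with accepted standard of care".
- Section 5.0 says that clinic patients aged 8 to 21 "will be asked to wear a Garmin VivoSmart 4 (or later) physical activity tracker for at least 6 months".
- Section 8.0 lists "1000 pre-screened for a total enrollment goal of 300", made up of 200 youth and 100 parents, with no comparison group.
- Section 12.0 says that "physical activity information will be collected from the participant trackers via the Garmin Connect app".

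**The concern.** In Objectives 2 and 3 the explanatory quantity is a measurement on each person: how active they were and how much they slept. In Section 28.1 it is membership of a group. These are different estimands, and the second is not among the listed objectives. The secondary objectives on change while wearing the tracker come closest, but they concern self-reported activity and fear of hypoglycemia over time, not a comparison with outside patients.

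If Section 28.1 were used to answer Objectives 2 and 3, they would go unanswered, or a difference between wearers and matched patients would be credited to physical activity. That difference mixes at least three things:

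- the tracker's prompts, which Section 6.0 describes as encouraging movement and reducing stress;
- any change in activity itself;
- selection. Section 7.2 excludes those unwilling to wear the device for 6 months, and Section 9.3 recruits partly on a predicted HbA1c rise of 0.3 points. Neither factor is in the propensity score.

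A null difference would be equally uninformative about whether more active participants do better.

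**Working it through.** The text gives no alpha, power, effect size, standard deviation, event rate, matching ratio or dropout, so there is no figure of the plan's own to reproduce. The check is mainly logical, with an illustration.

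**1. Objectives against analysis.**

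| | Explanatory quantity | Outcome |
|---|---|---|
| Objective 2 | measured activity and sleep | DKA admission rate |
| Objective 3 | measured activity and sleep | change in TIR and other CGM metrics |
| Objective 4 | Garmin variables as predictors | prediction of HbA1c change, DKA, TIR change |
| Section 28.1 | being in the tracker group | not named |

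**2. What is known about the matched patients.** All enrolled youth are asked to wear the tracker (Section 5.0). No other youth group is enrolled (Section 8.0). Garmin data come only from participants' trackers (Sections 5.0, 12.0 and 26.0). The matched cohort must then come from outside the enrolled youth, with no stated route for Garmin data on it. This is an inference, because the cohort is never defined.

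**3. Algebra.** Let *b* be the effect of one unit of activity on the outcome, *s* the amount by which wearing the tracker raises mean activity, and *g* every other effect of being in the tracker group. With perfect matching, the expected group difference is

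D = g + b × s.

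One number D cannot separate g, b and s. If a fraction p of matched patients also wore trackers, the expected difference becomes (1 − p) × (g + b × s), which does not isolate b either. So the conclusion does not depend on step 2.

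**4. Illustration (all inputs assumed).** There were 200 wearers and 200 matched controls, with 4,000 replicates. Mean activity was 45 in controls and 50 in wearers (s = 5), with SD 20. The outcome SD was 10. The value of g was set to D − 5b.

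| True b | g | True D | Mean matched difference | Mean within-wearer slope |
|---|---|---|---|---|
| 0 | 1.0 | 1.0 | 1.02 | 0.00 |
| 0.1 | 0.5 | 1.0 | 1.01 | 0.10 |
| 0.2 | 0 | 1.0 | 1.00 | 0.20 |
| 0.2 | −1.0 | 0 | −0.01 | 0.20 |

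The matched difference is the same whether activity explains none of it (row 1) or all of it (row 3). It is zero in row 4 although activity matters. The simulation contains no confounding of activity among wearers, so it shows what can be identified and does not show that a real within-wearer slope would be unbiased.

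**5. What each analysis could detect.** Assume two-sided alpha 0.05 and 80% power, so the normal quantiles sum to 1.960 + 0.842 = 2.802. For a 1:1 matched contrast with n per group, the detectable standardized difference is 2.802 × √(2/n). For a within-wearer correlation it is tanh(2.802/√(n − 3)).

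| n | Matched difference (SD units) | Within-wearer correlation |
|---|---|---|
| 200 | 0.28 | 0.20 |
| 150 | 0.32 | 0.23 |
| 100 | 0.40 | 0.28 |

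The two columns measure different quantities and are not rivals on precision. The last column applies approximately to a partial correlation with few covariates. It shows that a within-wearer analysis is workable for continuous outcomes at the planned size. It does not cover DKA, for which no event rate is given.

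**The case against.** The strongest reply is that Section 28.1 never claims to analyse Objectives 2 to 4. Its opening condition reads like a supplementary comparison, its numbering leaves room for further subsections, and the available text stops there. If a later subsection specifies within-wearer models, Section 28.1 is a reasonable extra. This stands in part. A reader might infer that the plan has no analysis for these objectives, and the documents do not support that inference. What remains is that Section 28.1 does not say which question it serves, and that it cannot serve Objectives 2 and 3.

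A reader might also take it as stated fact that the matched patients are non-wearers without Garmin data. The design and data flow imply it, but no passage says so, and the term for device usage in the propensity score is undefined. The conclusion holds either way.

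Objective 4 is not wholly unaddressed. Section 4.0, item 7, gives example performance measures, though no model, comparator or validation scheme, and nothing suggests that Section 28.1 was meant to serve it.

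It can also be said that misreporting a group difference as an activity effect is only a possibility. That is fair. However, Sections 15.0 and 16.0 themselves anticipate more activity and possible HbA1c improvement in response to the watch, so a plain statement of what the comparison means is worth having. Finally, the simulation result follows by construction; it illustrates the algebra and adds no independent evidence.

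**Conclusion.** The point holds in a limited form. The only analysis stated in Section 28, as far as the text runs, estimates the effect of being in the tracker group. It cannot estimate the impact of activity and sleep variables, so it answers neither of two of the four primary objectives (2 and 3). On the stated design, the information on those relations lies within the up to 200 youth wearers.

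The conclusion rests on the wording of Sections 2.1 and 28.1 and on the algebra, not on the assumed simulation inputs. It does not require that controls lack Garmin data, and it does not assert that other analyses are absent. Nor is the matched comparison wrong in itself: it is a legitimate supporting question about tracker-study participation, provided it is labelled as one.

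**What to change.** - **Section 28.1.** Label it a supporting comparison of tracker-study participation, not to be interpreted as the effect of physical activity. Name its outcomes, define the source and period of the cohort, and say what device usage means in the propensity score.
- **Objective 3, unless already specified elsewhere.** Among wearers with CGM data, regress change in TIR and the other CGM metrics at each horizon on mean daily MVPA and sleep over valid-wear days. Adjust for the baseline outcome value, age, diabetes duration, insurance and diabetes-device use. State the exposure window for each horizon. Add a participant random effect only if horizons are modelled jointly; with one change score per person per horizon it cannot be separated from residual error.
- **Objective 2, unless already specified elsewhere.** Use a count model for DKA admissions among wearers with a person-time offset, and few covariates if events are sparse.
- **Objective 4.** Compare predictive models of HbA1c change, DKA and TIR change with and without the Garmin variables, among wearers.
- **Exposure definition.** Settle the weighted MVPA formula in Section 5.0 before using it. As worded, the weights are 5/7 + 1/7 = 6/7, not 1. The valid-day rule counts daytime hours only, so sleep needs its own rule.

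The cost is plan wording and modest extra analysis. Enrolment and design do not change, and the data are already planned for collection. However, Section 26.0 allows fingerstick monitoring instead of CGM, so TIR may be missing for some participants. The results remain observational associations, open to confounding between activity and outcome.
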